2.2.7 Rituximab Biosimilars

Rituximab was first marketed in Europe under the brand name MabThera®. More recently, rituximab biosimilars have been launched (e.g. Rixathon® and Truxima®). It should be noted rituximab biosimilars may be used in this clinical trial (**Sponsor must be notified prior to use**) since they are licensed for use in the same indications and have the same expected safety profile as the originator product MabThera®. Therefore, any reference to rituximab throughout this protocol refers to both the originator product, MabThera® or an approved rituximab biosimilar.

For additional information concerning rituximab (or rituximab biosimilar), please refer to the SmPC specific to the brand used.

The rituximab SmPC included in the IB Package supplied for use in this trial is defined as the reference safety information (RSI) for all brands of rituximab used in this trial.

2.2.8 Expected safety profile for BI-1206 ± rituximab

Based on preclinical experience with BI-1206 alone and in combination with anti-CD20 antibodies (such as rituximab), emerging clinical data from the ongoing CRUKD/16/001 trial, reported clinical data regarding XmAb5871 and clinical experience of rituximab therapy, the potential toxicities associated with BI-1206 ± rituximab therapy could include the following:

- **Infusion related reactions** including CRS are a known, common side-effect of rituximab treatment and are an expected side effect of BI-1206 treatment. Symptoms could include rash, fever, rigors, bronchospasm, and hypotension. All patients will receive supportive care including pre-medication (see Section 5.9.2) and will be monitored before during and after infusion.
- **Side effects resulting from lymphodepletion and/or depletion of immune effector cells**, notably infections related to neutropenia and/or lymphopenia. Neutropenia is considered unlikely based upon the results of preclinical studies undertaken in two murine models that expressed hCD32b and hCD20 under the control of human promoters and on a mCD32b null background. These models demonstrated that BI-1206 ± rituximab selectively depleted B cells preferentially to other lymphoid or myeloid lineage cells. In the event these AE do manifest it is anticipated they will be readily manageable in the context of advanced B-cell malignancies. Haematology assessments conducted during the trial will include assessment of white blood cells (WBC) with differential count (eosinophils, basophils, neutrophils and lymphocytes) and B cell levels. Furthermore, patients who are Hepatitis (Hep) B, C or Human Immunodeficiency Virus (HIV) positive, or who have an active, ongoing infection or an active, known or suspected autoimmune disease will not be eligible for trial participation.
- **Effects on blood pressure**, Blockade of CD32b by BI-1206 could theoretically lead to treatment related changes in blood pressure. Blood pressure will be regularly monitored during the course of the trial and will be managed as required in line with local practice.

- **Thrombocytopenia/platelet count decreased.**
Included due to reported clinical data for the CRUKD/16/001 study. Laboratory test results are regularly monitored during the course of the trial and will be managed in line with local practice. Please see current version of IB for rate of occurrence.
- **Elevated transaminases.**
Included due to reported clinical data for the CRUKD/16/001 study. Laboratory test results are regularly monitored during the course of the trial and will be managed in line with local practice. Please see current version of IB for rate of occurrence.
- **Ocular toxicity** BI-1206 binding to the eye or spinal cord is unlikely given the limited potential that antibodies have to cross the blood brain barrier. However given their, albeit remote, potential to occur eye examinations have been included in the schedule of events to allow for assessment throughout study treatment. See Section 5.9.3 .
- **Tumour-lysis syndrome (TLS)** is a known, side effect of mAb therapy. Patients will be risk-assessed for TLS and receive supportive care as described in Section 5.9.1
- **Autoimmune disease.** From the observational studies in a murine CD32b^{-/-} transgenic model it has also been noted that CD32b inhibition is tolerated but there are certain, as yet unelucidated, genetic factors that can give rise to a profound autoimmune state in susceptible animals. The relevance of these factors to the proposed trial is expected to be limited by virtue of the short duration of CD32b inhibition by BI-1206 in vivo as compared to the life-long and total absence of CD32b in CD32b^{-/-} mice. Patients with active autoimmune disease (as defined in the protocol) will be excluded from the trial. Autoimmune assessments will be performed as clinically indicated.
- **Potential for an anti-drug antibody (ADA) response.** Despite the reported occurrence of MAHA in the murine toxicology studies the potential for neutralising antibodies directed against BI-1206 in trial patients is expected to be minimal by virtue of the fact that BI-1206 is a fully human antibody. Experience with other approved humanised therapeutic antibodies suggest an incidence of ADA ranging from <1% to over 30% [39, 40]. Neither the frequency nor the impact of these ADA (if observed) on the efficacy or tolerability of BI-1206 can be predicted ahead of the trial but will be monitored during the trial.
- **Combination effects.** The undesirable effects of rituximab are generally manageable when used as monotherapy or in combination with cytotoxic chemotherapy. In combination with BI 1206 these effects may be present and could be exacerbated. Patients will be monitored closely for exacerbation of known or suspected toxicities and for unexpected combination adverse effects

2.3 Rationale for the proposed trial

For the majority of patients, B-cell NHL and CLL are incurable using existing therapeutic approaches. Although anti-CD20 directed therapy has improved outcomes, very many patients still relapse following treatment or are refractory to it and therefore additional novel non-cross resistant therapies are required. The human CD20 mAb rituximab was the first mAb approved for cancer immunotherapy, and has been widely administered to patients with B-cell cancers including FL, DLBCL, CLL and MCL [41] in addition to an expanding number of autoimmune conditions. While rituximab is efficacious in FL and DLBCL, improving overall survival, only modest responses are seen in CLL and MCL. Furthermore, even in rituximab-responsive lymphoma sub-types some individuals show initial resistance or subsequently develop it.

BI-1206 is a fully-human anti-CD32b (Fc γ RIIB) antagonistic antibody that, in addition to directly killing tumour cells, is thought to work by prolonging anti-CD20 antibody residence on the cell membrane of cancer cells, preventing them from becoming resistant to treatments such as rituximab. It is anticipated that BI-1206 will have appreciable single agent activity but that the main likely clinical use will be in combination with rituximab and other sensitive antibodies preventing their internalisation by Fc γ RIIB and thereby augmenting their activity. Consequently, the clinical trial has been designed to allow

evaluation of the tolerability of BI-1206 as a single agent but also to partner BI-1206 with an anti-CD20 antibody at the earliest possible opportunity. Rituximab has been chosen as the most appropriate anti-CD20 antibody for use in combination at the start of this trial (see Section 2.2.6).

To evaluate these two possible modes of action, BI-1206 will be examined as a monotherapy in Arm 1, and concurrent administration of BI-1206/rituximab will be investigated in Arm 2 in both Parts A and B of the trial.

In the CRUKD/16/001 clinical trial, dose escalation phase (Part A), CD32b expression will be measured for information only; results will not be used as part of the eligibility criteria. The primary endpoints for this phase of the trial are safety and tolerability. CD32b expression will therefore be captured during study screening assessments to permit retrospective correlation of CD32b status (positive or negative) with the frequency and nature of any BI-1206 related toxicities, to further clarify the mechanistic pharmacology of CD32b inhibition.

The expansion phase (Part B), will be an expansion cohort of selected patients expressing the CD32b target and therefore form part of the eligibility criteria. Data from samples analysed from treated patients in Part A will be used to refine pre-screening selection requirements for Part B.

3 TRIAL DESIGN

3.1 Clinical trial objectives and endpoints

3.1.1 Primary objectives and endpoints

Primary objectives	Endpoints
Part A Escalation phase	
Arm 1: To propose a recommended dose for Phase II evaluation of BI-1206 as a single agent in by:	
(a) Establishing the maximum tolerated dose (MTD) or maximum administered dose (MAD) of BI-1206 given once weekly for four weeks, via intravenous infusion in patients with relapsed or refractory B-cell malignancies in Part A only.	(a) Determining the maximal dose (up to 800 mg) of BI-1206 at which no more than one patient out of up to six patients at the same dose level experience a highly probably or probably BI-1206 related dose-limiting toxicity during induction therapy and up to one week post the fourth infusion.
(b) Assessing the safety and toxicity profile of BI-1206 as a single agent in Part A and Part B	(b) Documenting adverse events (AEs), serious adverse events (SAEs) (graded according to NCI-CTCAE Version 4.02) and laboratory parameters and determining their causality in relation to BI-1206. Causality of AEs/SAEs will be assessed by the Investigator.
Arm 2: To propose a recommended dose for Phase II evaluation of BI-1206 in combination with an anti-CD20 antibody by:	
(c) Establishing the MTD or maximum administered dose MAD of BI-1206 and an anti-CD20 antibody given once weekly for four weeks, via intravenous infusion in patients with relapsed or refractory B-cell malignancies in Part A only.	(c) Determining the maximal dose (up to 800 mg) of BI-1206 at which no more than one patient out of up to six patients at the same dose level experience a highly probably or probably BI-1206 or anti-CD20 antibody-related dose-limiting toxicity during induction therapy and up to one week post the fourth infusion.
(d) Assessing the safety and toxicity profile of BI-1206 in combination with an anti-CD20 antibody in Part A and B.	(d) Documenting AEs, SAEs (graded according to NCI-CTCAE Version 4.02) and laboratory parameters and determining their causality in relation to BI-1206 and, where appropriate, anti-CD20 antibody. Causality of AEs/SAEs will be assessed by the Investigator.
Part B Expansion phase	
Assessing the safety and toxicity profile of: 
• BI-1206 as a single agent in Arm 1 at the RP2D as determined in Part A (Part B, Arm 1)• BI-1206 when given in combination with an anti-CD20 monoclonal at the RP2D combination dose as determined in Part A (Part B, Arm 2)	Documenting AEs, SAEs (graded according to NCI-CTCAE Version 4.02) and laboratory parameters and determining their causality in relation to BI-1206 and, where appropriate, anti-CD20 antibody. Causality of AEs/SAEs will be assessed by the Investigator.

3.1.2 Secondary objectives and endpoints

Secondary objectives	Endpoints
Parts A and B	
To determine the PK profile of BI-1206 (\pm an anti-CD20 mAb) as a single agent in patients with relapsed or refractory B cell malignancies.	Measurement of PK parameter values for BI-1206 (as a single agent and when given in combination with an anti-CD20 monoclonal antibody) during the BI-1206 treatment period including AUC, C_{max} , T_{max} , and half-life ($T_{1/2}$) in serum samples using enzyme-linked immunosorbent assay (ELISA).
To assess the immunogenicity of BI-1206 (\pm an anti-CD20 mAb) in patients with relapsed or refractory B cell malignancies.	Measurement of anti-drug antibody (ADA) response to BI-1206 (as a single agent and when given in combination with an anti-CD20 mAb) during the BI-1206 treatment period using ELISA.
To evaluate the effect of BI-1206 (\pm an anti-CD20 mAb) on the depletion of peripheral blood B cells (B lymphocytes).	Measurement of peripheral blood B-lymphocyte depletion during the BI-1206 treatment period (as a single agent and when given in combination with an anti-CD20 mAb) using flow cytometry.
To document possible anti-tumour activity of BI-1206 (\pm an anti-CD20 mAb) in patients	Assessment of best disease response according to the revised response criteria for malignant lymphoma (Cheson, 2014) Waldenström macroglobulinaemia assessment criteria (Owen 2013, Kimby 2006) or NCI chronic lymphocytic leukaemia (CLL) criteria (Hallek, 2008).
To measure the duration of response to BI-1206 (\pm an anti-CD20 monoclonal antibody) over a follow-up period of 1 year.	Measure progression free survival (PFS) and overall survival (OS) at 1 year after the first BI-1206 administration on the study for all patients.

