3.5.5 Survival

All patients receiving at least one administration of mAb (BI-1206 with/without rituximab) as part of this trial will be evaluable for survival (OS and PFS) regardless of whether they subsequently receive other anti-cancer treatments. Please see Section 7.5.2.

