10.3 Timing and type of tumour assessments

A thorough evaluation of malignancy, as judged appropriate by the Investigator, and in line with the protocol, must be performed before a patient receives their first dose of BI-1206 or rituximab. The same methods that detect evaluable lesions at baseline must be used to follow these lesions throughout the trial. To ensure compatibility, radiological assessments used to assess response must be performed using identical techniques. Imaging based evaluation is preferred to evaluation by clinical examination when both methods have been used to assess the anti-tumour effect of a treatment.

All radiological assessments must be performed within four weeks before starting treatment with BI-1206 or rituximab. The interval between the last anti-cancer therapy and these measurements must be at least four weeks (28 days). All clinical measurements to assess response must be performed within **one** week prior to a patient's first dose of BI-1206.

Copies of the scans must be available for external independent review if requested by Cancer Research UK's Centre for Drug Development (CDD).

All patients will be evaluated at baseline, four weeks after the last dose of BI-1206 or rituximab on study, every 16 weeks (\pm 2 weeks) during their maintenance phase and at off-study, unless progression occurs at an earlier time point, at which the patient will be evaluated instead.

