13.5 Anti-tumour activity

Documenting anti-tumour activity is a secondary objective of this trial. Patients must receive at least one dose of BI-1206 and/or rituximab on as part of this trial; have a baseline disease assessment and at least one follow-up disease assessment to be evaluable for response. Patients who experience clear clinical disease progression without formal post-treatment disease assessment will be included and will be considered to have progressive disease. Objective responses, the best tumour response achieved by each patient while on trial and the time to progression will be presented in the data listings.

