13.6.2 Progression-Free Survival

All patients who receive BI-1206 and/or rituximab as part of this study and who complete a baseline and at least one post-treatment disease assessment (or experience clear disease progression without a formal post-treatment disease assessment) will be evaluable for progression-free survival (PFS), regardless of whether they subsequently receive other anti-cancer treatments. PFS will be measured from the date of administration of the first dose of BI-1206. Subgroup analyses of per protocol patients may be performed. Median progression free survival will be reported. Patients who are lost to follow-up will be censored at the time of last recorded disease assessment, patients who start a new treatment will not be censored.

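### The PFS population in Section 13.6.2 conflicts with Sections 3.1.2 and 3.5.5, and the duration-of-response objective is paired with an endpoint that does not measure it

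*Combined protocol and SAP*

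**What the plan says.** **Objective and endpoint.** The last secondary objective in Section 3.1.2 begins "To measure the duration of response to BI-1206" and sets a one-year follow-up. Its endpoint is "Measure progression free survival (PFS) and overall survival (OS) at 1 year after the first BI-1206 administration on the study for all patients".

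**PFS population, first statement.** Under Section 3.5.5, everyone given at least one dose of antibody "will be evaluable for survival (OS and PFS) regardless of whether they subsequently receive other anti-cancer treatments". No disease assessment is required.

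**PFS population, second statement.** Section 13.6.2 restricts PFS to treated patients "who complete a baseline and at least one post-treatment disease assessment", with an exception for clear progression that was not formally assessed. Time runs from the first BI-1206 dose. On censoring it says: "Patients who are lost to follow-up will be censored at the time of last recorded disease assessment". On reporting it says: "Median progression free survival will be reported". It does not list the PFS events.

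**Death as an event.** The only definition of PFS that names death is in the CLL response criteria reproduced in Appendix 4 (item 5.6). There the clock starts at study entry.

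**Response output.** Section 13.5 says that objective responses, "the best tumour response achieved by each patient while on trial and the time to progression will be presented in the data listings". No readable section defines or summarises duration of response. Section 3.1.3 is redacted, but it holds tertiary objectives and this one is secondary.

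**The concern.** There are two drafting faults.

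First, the protocol states the PFS population twice, and the statements differ for a group that is not random: treated patients who die early, for example from infection or toxicity, without documented or clear progression. Leaving them out removes failures from the denominator. The trial is open label, so if the conflict stays, someone chooses between the two populations after the data are visible. The missing event definition adds to this. For patients without CLL, nothing says how a death without progression enters PFS, whether it comes early or late.

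Second, the objective names duration of response, which exists only for responders and starts at response. The paired endpoint covers all patients and starts at first dose. PFS does move with response duration, but it also depends on the response rate and on how fast non-responders progress. A report that follows Section 3.1.2 literally would present PFS and OS as the answer to a different question.

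**Working it through.** The documents give no figure to reproduce. Section 13.1 makes the analysis descriptive, with no power, alpha or event count. The check is a comparison of the rules, followed by an illustration of size.

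**1. The rules applied to four treated patients**

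| Treated patient | Section 3.5.5 | Section 13.6.2 |
|---|---|---|
| Has baseline and Week 8 assessments | In | In |
| Clear progression, never formally assessed | In | In |
| Dies before Week 8 without clear progression | In | Out |
| Lost before Week 8, event-free, no post-treatment assessment | In | Out |

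The third and fourth rows cannot be reconciled. The OS population in Section 13.6.1 agrees with 3.5.5, so 13.6.2 is the outlier.

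**2. Which excluded patients matter.** A patient censored at first dose leaves the risk set at time zero, so the Kaplan-Meier curve is the same with or without that patient. The fourth row is therefore harmless if handled that way. Only the early deaths move the estimate.

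**3. Effect on 12-month PFS.** Take n treated patients, no censoring before 12 months, and d excluded early deaths that would otherwise count as events. Then:

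PFS after exclusion = PFS × n/(n − d)

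The factor exceeds 1 whenever d > 0, so the shift is always upward. Take n = 25, the ceiling for one expansion arm (Sections 5.7 and 5.8), and assume 6 patients event-free at 12 months:

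- d = 0: 6/25 = 24.0%, exact 95% interval 9.4% to 45.1%
- d = 1: 6/24 = 25.0% (factor 25/24 = 1.042)
- d = 2: 6/23 = 26.1% (factor 25/23 = 1.087)

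**4. Effect on the median, which is what Section 13.6.2 reports.** Assume exponential PFS with a 6-month median and no censoring. With 25 patients the median is the 13th ordered time. Dropping two early deaths makes it the 14th of the original 25; dropping one makes it the average of the 13th and 14th. The expected gap between the two is (6/ln 2)/12 = 8.66/12 = 0.72 month. The median therefore rises by about 0.36 month (d = 1) or 0.72 month (d = 2). Simulation agrees: typical sample medians are 6.0, 6.4 and 6.7 months for d = 0, 1 and 2, and the sample median itself has a 95% range of 3.2 to 10.0 months.

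**5. How many early deaths.** The first post-treatment assessment is at Day 50, with up to one week more (Section 7.6). Section 2.1.1 quotes background median survival of about 12 months (CLL) and 13 months (lymphoma). Assuming exponential survival:

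P(death before assessment) = 1 − 0.5^(t/median)

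- t = 50 days, median 13 months: 8.4%, or 2.1 of 25
- t = 57 days, median 12 months: 10.3%, or 2.6 of 25

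This is an upper bound on exclusions through death. Patients with clear progression stay in, and inclusion criterion 4 asks for a life expectancy of at least 12 weeks (84 days), which is beyond Day 57. One or two excluded deaths per arm is therefore a reasonable range to illustrate, not a forecast.

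**The case against.** The strongest reply is that the excluded group is small and already protected. Section 10.3.1 and the closing text of 10.3.3 require patients removed for reasons other than progression to be re-evaluated at discontinuation, unless they were assessed in the previous four weeks. Section 7.4 asks for a disease assessment at the off-study visit where possible. Section 13.6.2 keeps clear progression without formal assessment, and the 12-week life-expectancy criterion selects against very early death. All of this stands and limits the size. None of it covers a patient who dies before assessment without clear progression.

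Several stronger readings are tempting, and the documents do not support them:

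- **PFS times can be negative.** A reader might infer this, because a patient with no post-baseline assessment has baseline as the last one, and on baseline imaging Section 10.3 says "All radiological assessments must be performed within four weeks before starting treatment with BI-1206 or rituximab". It happens only if the 3.5.5 population is joined to the 13.6.2 censoring rule. Under 13.6.2 as written, that patient is outside the PFS set. It is a reason to change the censoring rule together with the population, not a separate defect.
- **Death is nowhere a PFS event.** Appendix 4 says that it is for CLL, and CLL supplies at least 12 of up to 25 patients per expansion arm. The gap is in 13.6.2 and for the other diseases, together with the different start of the clock.
- **Duration of response cannot be recovered.** Best response is its own secondary endpoint, response is recorded at each visit with a disease assessment (Section 10.4.4), and time to progression is listed. A reader need not infer duration from a single PFS value and could derive it from the listings. What is missing is a definition and a planned summary.
- **Medians contradict an endpoint set at one year.** The phrase can mean the length of follow-up, as in Section 7.5.2, and need not call for a one-year rate. Adding that rate is a reporting preference.

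**Conclusion.** The concern holds as a minor point. Sections 3.5.5 and 13.6.2 give PFS populations that cannot both be used, and the all-patients wording in 3.1.2 sides with 3.5.5. Following 13.6.2 can only raise PFS when the dropped patients are early deaths that would count as events. On assumed counts the rise is one to two percentage points at 12 months, or about 0.4 to 0.7 month on a 6-month median, well inside the sampling error of a 25-patient arm. Those sizes rest on no censoring before 12 months, one or two excluded deaths and, for the median, exponential PFS. The direction does not depend on the exponential model.

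The event definition is incomplete outside CLL, and the CLL appendix and 13.6.2 start the clock at different points. The duration-of-response objective is mislabelled or lacks its analysis.

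A reader might infer a material bias in the efficacy results. The documents do not support that: the endpoint is secondary and descriptive, the stated dose-escalation and recommended-dose rules do not use PFS, and the primary objectives are unaffected. The case for acting is that the choice should be fixed before the data are seen, and that fixing it is nearly free.

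**What to change.** **In Section 13.6.2:**

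- Use all treated patients, as in 3.5.5.
- Count progression or death from any cause as the event for every disease, and say that this governs over the Appendix 4 excerpt.
- Keep the first BI-1206 dose as the start of the clock.
- Censor event-free patients with no post-baseline assessment at first dose. The wider population makes this rule necessary.

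**In Section 3.1.2, choose one:**

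- Relabel the objective as PFS and OS; or
- Keep duration of response and add a descriptive summary to 13.5: time from first documented response to progression or death, among responders, by arm. State whether a minor response counts in Waldenström's disease, and when the clock starts for a CLL partial remission, which Appendix 4 requires to be documented for two months.

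One-year Kaplan-Meier estimates with intervals beside the medians are optional.

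**Cost.** The change is wording in three sections and a few table rows. Response, disease status and survival are already collected (Sections 7.5.2 and 10.4.4), so no visit, scan or patient is added. PFS will look slightly less favourable. Any duration-of-response summary would rest on few patients: at assumed response rates of 10% to 40%, 25 × 0.10 = 2.5 to 25 × 0.40 = 10 responders per arm, with progression dated coarsely by 16-weekly scans during maintenance.
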